In a study comparing auscultation, capnometry and capnography for endotracheal tube confirmation, Grmec¹² found that auscultation is unreliable compared to capnometry and capnography. While the sensitivity and specificity of capnography were both 100% in 345 emergency intubations including both cardiac arrest and non-arrest patients, the sensitivity and specificity of capnometry were 88% and 100% respectively. In their study, there were 28 false negatives in capnometry which were all cardiac arrest cases. Similar results showing better reliability of capnography over capnometry was found by Ornato et al¹³, Macleod et al¹⁴, and Bozeman et al¹⁵.

A continuous, stable CO₂ waveform ensures the presence of alveolar ventilation but does not necessarily indicate that the endotracheal tube is properly positioned in the trachea. Endotracheal tube placed proximally to the vocal cords may still produce an otherwise satisfactory tracing until it becomes dislodged. An endobronchial intubation cannot be ruled out until breath sounds are auscultated bilaterally. Capnography is also unreliable for endotracheal tube confirmation during low pulmonary flow states, and also during bronchospasm or a kinked endotracheal tube.⁴ Though the American Heart Association (AHA) has incorporated presence of capnograph waveforms and ETCO₂ value greater than 10 mm of Hg as sign of effective chest compressions in the Advanced Cardiac Life Support (ACLS) algorithm¹⁶; capnography is regarded to be unreliable during cardiopulmonary resuscitation^{1,2,7} and also with adrenaline use.⁶

[figure not shown]

Fig. 2. Normal waveform capnogram during tracheal intubation.^{8(p1554)}

[figure not shown]

Fig. 3. Irregular waveform capnogram during oesophageal intubation.^{8(p1554)}

Ultrasonography

Ultrasonography is now being increasingly used in medical practice as a bedside point of care utility. It is safe, quick in learned hands, portable and widely available in different departments of a hospital or other health facilities.¹⁷ Applications of ultrasound imaging in airway management can be as follows^{17,18}:

- Identification of position of endotracheal tube during intubation
- Assessment of the diameter of the subglottic upper airway and prediction of endotracheal tube size, including pediatric endotracheal tube size and double-lumen tube size
- Detection of subglottic stenosis, prediction of post-extubation stridor
- Guidance of percutaneous dilatational tracheostomy and cricothyroidotomy

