Grmec¹² also found similar results as that of Knapp et al²⁶ when comparing auscultation, capnometry and capnography for endotracheal tube confirmation. He tested 345 emergency intubations in a prehospital unit at Maribor, Slovenia from February 1998 to February 2001. 246 were cardiac arrest patients and 79 were non-cardiac arrest patients. In non-arrest patients, capnometry had both sensitivity and specificity of 100%; capnography also had both sensitivity and specificity 100% but auscultation had sensitivity of 94% and specificity of 83% in confirming endotracheal tube placement. Capnometry was highly specific (100%) but not sensitive (88%) for correct endotracheal intubation in patients with cardiopulmonary arrest while capnography again had both sensitivity and specificity of 100%. They concluded that capnography was the most reliable method to confirm endotracheal tube placement in emergency conditions in the prehospital setting.¹²

A meta-analysis was done by Li²⁴ on the use of end tidal CO₂ detection methods for endotracheal tube confirmation. 512 trials were processed from the National Institute of Health (USA) database from 1996 to 1999. Trials that included human subjects in whom emergency endotracheal intubation had been done, where the tube position was checked by a device measuring end tidal CO₂ and the result compared with another method of verification of tube position as standard, were chosen. He also excluded trials where number of tracheal and oesophageal intubations were not shown as part of the secondary objective. 10 trials were finalized and 2192 intubation were included. Tube placement for 444 out of 2192 intubations (20%) had been tested with infrared devices, and placement for 1748 out of 2192 intubations (80%) had been tested with colorimetric devices. The results showed an aggregate sensitivity of 93% (95% confidence interval (CI): 92 – 94%) and an aggregate specificity of 97% (95%

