intubation attempts. Tracheal ultrasonography was used in ten studies and lung ultrasonography was used in four studies, two studies used both tracheal and lung ultrasonography to confirm endotracheal tube placement. Seven studies used capnography or ETCO₂ detectors as criterion standard of tracheal intubation whereas the remaining studies used direct laryngoscopy, chest auscultation, or chest radiography. For detection of oesophageal intubation, the pooled sensitivity of ultrasonography was 0.93 (95% CI: 0.86–0.96) and the specificity was 0.97 (95% CI: 0.95–0.98). The positive and negative likelihood ratios were 26.98 (95% CI: 19.32–37.66) and 0.08 (95% CI: 0.04–0.15) respectively. A hierarchical summary receiver operating characteristic curve that plots sensitivity versus specificity was constructed and the area under the curve was calculated to be 0.97 (0.95–0.98). In tracheal ultrasonography, attending physicians demonstrated superior sensitivity (0.98, 95% CI: 0.96–0.99) when compared to resident physicians (0.92, 95% CI: 0.78–0.96). Tracheal ultrasonography performed in the emergency had a lower sensitivity (0.88, 95% CI: 0.76–0.94) in comparison to other settings. Tracheal ultrasonography performed in real-time was associated with superior sensitivity (0.94, 95% CI: 0.86–0.98) than that performed post-intubation in static manner (0.91, 95% CI: 0.70–0.98). They concluded that ultrasonography had high diagnostic value for identifying oesophageal intubation. They recommended ultrasonography be used as a valuable adjunct in endotracheal intubation confirmation, especially in situations where capnography may be unreliable.⁶

A systematic review and meta-analysis was also done by Das et al²¹ in 2015 to evaluate the diagnostic accuracy of transtracheal ultrasound in detecting endotracheal intubation. Eleven studies and 969 intubations were included in the final analysis.

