Participants were also excluded if there was:

- Unanticipated difficult bag and mask ventilation
- Unanticipated difficult intubation or CL grade 3 and 4 cases, use of bougie for intubation.
- Fall in Spo₂ (< 90%) before endotracheal tube position confirmation
- Bradycardia (heart rate < 40 beats/min) or hypotension (mean arterial pressure < 60 mm of Hg, systolic blood pressure < 80 mm of Hg) during or prior to intubation
- Tachycardia more than 120 bpm or blood pressure more than 180 mm Hg systolic or 110 mm Hg diastolic during or prior to intubation

There were 36 participants enrolled at MCVTC, out of which 5 of the participants had to be excluded out of the study. One had unanticipated difficult intubation, and the other four had hypotension after induction of anaesthesia. There were 67 participants

enrolled at TUTH, out of which 3 participants had to be excluded out of the study. Two subjects had hypotension after induction of anaesthesia. The other one had to be excluded because the ultrasound machine went into hung state. Thus there were 31 subjects from MCVTC and 64 subjects from TUTH. Data collection was terminated once the sample size of 95 was met. Different individuals operated ultrasound on the subjects in this study. Flow diagram of the study is shown in figure 8.

Operational Definitions

Ultrasound positive: meant ultrasound detected tracheal intubation. There was fluttering and movement inside the tracheal acoustic shadow as the endotracheal tube was passed, and by the completion of intubation there was only one comet tail appearing acoustic shadow. Color Doppler ray showed color change inside the acoustic shadow on shaking the endotracheal tube.

Ultrasound negative: meant ultrasound detected oesophageal intubation. There was fluttering and increase in echogenicity in the region of oesophagus as the endotracheal tube was passed. By the completion of intubation, there were two comet tail appearing acoustic shadows, “double-tract sign”. Color Doppler ray was seen outside the trachea on shaking the endotracheal tube.

Capnograph positive: meant capnogram showed regular normal shaped waveforms after 6 ventilations. The outcome was tracheal intubation.

Capnograph negative: meant oesophageal intubation. The capnogram had no waveforms or irregular, bizarre or non-uniform shaped waveforms after 6 ventilations.

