Hence these descriptive variables did not affect the outcome of the study. These variables reflect the demographic profile of the patients served at the academic centres of IOM in Maharajgunj and provide validity to the study. This data could help as reference for researchers who might carry out similar studies in the same centres in future.

Analytical Statistics

The incidence of oesophageal intubation was 11.57% in this study. Reported incidence of oesophageal intubations during elective intubation is less than 2%.^{12,39}

The incidence of oesophageal intubation increases up to 6 - 16 % during in-hospital emergency intubations.^{29,30,39,40}

Ultrasonography

In this study, the sensitivity, specificity, positive predictive value and negative predictive value (with their corresponding 95% confidence intervals) of ultrasonography were calculated to be 97.62% (91.66% - 99.71%), 90.91% (58.72% - 99.77%), 98.80% (92.67% - 99.81%) and 83.33% (55.66% - 95.22%) respectively.

The sensitivity of ultrasonography in this study is comparable to sensitivity reported in the meta-analyses done by Das et al²¹ and Chou et al⁶, which were 98% and 93% respectively. The specificity was 90.91% in this study, which is slightly lower compared to the above mentioned meta-analyses where specificity ranges from 97 to 98%.^{6,21} But the 95% confidence interval of specificity in this study extends from 58.72 to 99.77% which covers the reported specificity 97 to 98% in these meta-analyses. Thus the calculated pretest probabilities of ultrasonography in this study were not different from those reported in literature.

The PPV and NPV of ultrasonography calculated in this study were 98.8% and 83.33% respectively. The PPV of ultrasonography in this study is similar to that found by Adi et al³⁰, Chou et al²⁸, Chintamani et al³⁴ and Nasreen et al³³: the reported PPV ranges from 98 to 100% in these studies. The NPV of ultrasonography has been reported to be: 62.5% by Chintamani et al³⁴, 75% by Adi et al³⁰, 94% by Chou et al²⁸, and 96.77% by Nasreen et al³³. The 95% confidence interval of NPV of ultrasonography in this study was (55.66%- 95.22%), which is comparable to the NPV found by the above mentioned studies.

Ultrasonography had an accuracy of 96.84% in endotracheal tube confirmation in this study. Similar accuracy ranging from 97 to 98% had also been found by previous researchers.^{28,30,33}

There are various ways of using ultrasonography for endotracheal tube confirmation.

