The median operating time of static post-intubation ultrasound was found to be 9 seconds with IQR [6 – 14 sec] by Chou et al²⁸ in their study. This was significantly faster than transcricothyroid static ultrasound for endotracheal tube confirmation done by Adi et al³⁰; their median time was 16.40 seconds. The results of these studies cannot be compared with this study because the beginning of laryngoscopy was taken as the start point for time assessment in this study. These studies started their assessment after intubation. The time for laryngoscopy is directly operator dependent and thus the time taken for assessment of endotracheal tube position directly increases with more time spent on doing laryngoscopy and intubation in this study.

Capnography

The sensitivity and specificity of capnography to detect endotracheal tube position was found to be 96.43% and 100% respectively in this study. This was similar to aggregate sensitivity and specificity of 93% and 97% found by Li in his meta-analysis.²⁴ This meta-analysis included trials which used any form of end tidal CO₂ detection device in adult human subjects. We have used only waveform capnography which is the gold standard; colorimetric and quantitative ET_{CO}₂ are less accurate than waveform capnography.^{3,7,8,12}

There were three false negative results in capnography. Two of the three false negative results occurred while using sidestream capnography at TUTH and the other false negative result occurred at MCVTC which also had sidestream capnography. There were more than two irregular waveforms during the first six ventilations in these false negative cases.

The false negatives might have occurred in the sidestream capnographs because these are more likely to be blocked due to fogging or misting^{2,7} such that the sampling line gas flow could have been obstructed. At MCVTC, after about 15 irregular waveforms, there was no waveform seen for about the next 90 seconds followed by presence of regular waveforms thereafter. This might be due to auto calibration of the capnograph, the occurrence of which during intubation might have produced false negative result.

Other causes like compromised pulmonary blood flow and bronchospasm can also lead to false negative results.^{3,9,10} Patients who had hypotension after induction of anaesthesia that could lead to compromised pulmonary flow, were excluded from this study. Bronchospasm would be identified by auscultation or high peak airway

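### The Discussion sets ultrasound accuracy for tracheal placement beside one meta-analysis's figures for detecting oesophageal intubation, and infers agreement with the literature from 11 oesophageal tubes

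*Combined protocol and SAP*

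**What the plan says.** Operational Definitions: "Ultrasound positive: meant ultrasound detected tracheal intubation". Table 1 follows this coding, so sensitivity is the share of tracheal tubes called tracheal and specificity the share of oesophageal tubes called oesophageal.

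Literature Review, ultrasound meta-analysis of 12 studies (reference 6): "For detection of oesophageal intubation, the pooled sensitivity of ultrasonography was 0.93", with specificity 0.97. The meta-analysis of 11 transtracheal studies (reference 21) is described as addressing endotracheal intubation, with pooled values 0.98 and 0.98.

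Discussion, Ultrasonography: sensitivity is compared with 98% (reference 21) and 93% (reference 6). Specificity is called "slightly lower compared to the above mentioned meta-analyses where specificity ranges from 97 to 98" per cent. Because the interval covers those values, the text concludes: "Thus the calculated pretest probabilities of ultrasonography in this study were not different from those reported in literature". The NPV interval, printed as 55.66-95.22%, is set against four published values (62.5%, 75%, 94%, 96.77%) and described as one "which is comparable to the NPV found by the above mentioned studies".

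Discussion, Capnography: of 96.43% and 100%, "This was similar to aggregate sensitivity and specificity of 93% and 97% found by" a meta-analysis of exhaled-CO2 devices (reference 24). The Literature Review says of that pool that "placement for 1748 out of 2192 intubations (80%) had been tested with colorimetric devices". The Introduction also cites a waveform series (reference 12): "While the sensitivity and specificity of capnography were both 100% in 345 emergency intubations".

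**The concern.** Sensitivity and specificity change places when the target condition is reversed. A source reported for oesophageal detection must be swapped before it is set beside results coded for tracheal placement. The Discussion does not swap it, so the literature range is wrong for both measures.

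A second problem lies in the inference. An interval that covers a benchmark shows only that the data do not exclude it. With 11 oesophageal tubes the interval would cover almost any plausible benchmark.

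These sentences are the study's external check on both tests. A reader may take them as confirmation that the tests performed here as they do elsewhere.

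**Working it through.** **Reproducing the study's figures.** Inputs are Tables 8 and 9; intervals are Clopper-Pearson, the method named in the Methodology.

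| Measure | Count | Estimate | Exact 95% interval | Printed |
|---|---|---|---|---|
| Ultrasound sensitivity | 82/84 | 97.62% | 91.66-99.71% | same |
| Ultrasound specificity | 10/11 | 90.91% | 58.72-99.77% | same |
| Capnography sensitivity | 81/84 | 96.43% | 89.92-99.26% | same |
| Capnography specificity | 11/11 | 100% | 71.51-100% | same |
| Ultrasound NPV | 10/12 | 83.33% | 51.6-97.9% | 55.66-95.22% |

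The first four reproduce. The NPV interval does not.

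**Re-orienting reference 6.** For oesophageal detection it gives 0.93 and 0.97. With trachea as positive, sensitivity is 0.97 and specificity 0.93. Reference 21 stays at 0.98 and 0.98.

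| | Range used in the Discussion | Range with matched target |
|---|---|---|
| Sensitivity | 93-98% | 97-98% |
| Specificity | 97-98% | 93-98% |

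Specificity shortfall as written: 97 − 90.91 = 6.09 to 98 − 90.91 = 7.09 points. After matching: 93 − 90.91 = 2.09 to 7.09 points. Sensitivity of 97.62% falls inside 97-98%.

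Exact binomial tests agree. Specificity gives p = 0.55 against 0.93 and 0.20 against 0.98. Sensitivity gives p = 1.00 against 0.97 and 0.69 against 0.98. The specificity interval covers every benchmark before and after the swap.

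**What 11 tubes can show.** If true specificity were 70%, P(at least 10 of 11 correct) = 11 × 0.70^10 × 0.30 + 0.70^11 = 0.0932 + 0.0198 = 0.113. A result this good would arise about one time in nine from a test with clearly poor specificity.

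**NPV.** The published value of 96.77% lies outside the printed interval but inside the Clopper-Pearson interval, 51.6-97.9%. The Methodology also prints a normal-approximation formula. For 10/12 it gives 0.8333 ± 1.96 × √(0.8333 × 0.1667 / 12) = 0.8333 ± 0.2109, or 62.2% to 104.4%. The printed interval matches neither.

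**Capnography.** Colorimetric share of the pool: 1748/2192 = 79.7%. All its trials were of emergency intubation. The waveform series reports 100% and 100%, but was prehospital and mostly cardiac arrest (246 arrest, 79 non-arrest; these sum to 325, not 345). Its number of tracheal tubes is not given. Fisher exact tests of 3/84 missed here:

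- against 0 of 276 to 345 (assumed range, arrest and non-arrest pooled): p = 0.012 to 0.007;
- against 0 of 79 (the most the non-arrest group could supply): p = 0.25.

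**The case against.** The strongest reply is that nothing turns on this. Only one of two benchmarks is crossed, the correction moves the study closer to the literature, and no objective or hypothesis depends on published values. This largely stands: the ultrasound result is not weakened by the swap. The printed ranges remain wrong, however, and the claim of no difference remains unsupported whichever orientation is used.

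It can also be said that the replacement pair should not be settled until the Methodology is reconciled. The Sample size paragraph credits reference 6 with 0.98 and 0.94, against 0.93 and 0.97 in the Literature Review. The 0.98 and 0.94 equal the emergency figures given for reference 21, so a misattribution is likely. That is fair and belongs in the fix.

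Two stronger readings are tempting and are not supported.

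- *A reader might infer that the NPV sentence is refuted because 96.77% lies outside the interval.* The interval by the named method contains it. The fault is in the printed interval.
- *A reader might infer that capnography performed below its like-for-like benchmark.* An exact upper limit below 100% carries no weight, since any single miss produces one (83/84 gives 99.97%). The waveform series matches on device but not on setting. The small p-values need an assumed denominator and the pooling of arrest patients; against the non-arrest patients p is about 0.25, which does not show equivalence either. The Discussion itself says that the pool covered any CO2 device and that colorimetric readings are less accurate. The Literature Review reports two trials (721 intubations) with no accuracy difference between colorimetric and infrared devices, and a review in which no method reached 100% on both measures.

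**Conclusion.** The crossed benchmark is established from the documents' own text. It affects reference 6 only. The literature ranges should read 97-98% for sensitivity and 93-98% for specificity, and observed specificity is about 2 to 7 points below the latter. This rests on the Literature Review's account of reference 6; the Sample size paragraph gives other values for the same source.

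The conclusion that accuracy is no different from the literature is not supported for specificity. With 10 of 11 and an interval of 58.72-99.77%, the data can neither confirm nor refute agreement.

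The NPV interval needs recomputing. Calling capnography similar to the pooled figures needs qualifying, because the pool was 80% colorimetric and all emergency. Neither matter shows a shortfall in test performance. These are faults of reporting and interpretation; design, data and the study's own estimates of sensitivity and specificity are unaffected.

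**What to change.** 1. Discussion, Ultrasonography: restate reference 6 as sensitivity 97% and specificity 93% for tracheal placement, and give the literature ranges as 97-98% and 93-98%.
2. Reconcile the Sample size paragraph with the Literature Review on which source supplied 0.98 and 0.94.
3. Replace the claim of no difference with a statement that specificity is too imprecisely estimated to compare (11 oesophageal tubes, 58.72-99.77%).
4. Recompute the NPV interval by Clopper-Pearson (10/12: 51.6-97.9%) and correct it in the Abstract, Results, Table 10 and Discussion. Keep the comparison with published values, reworded to reflect the interval's width.
5. Discussion, Capnography: state that the pool was 80% colorimetric and all emergency. Report the waveform series (100% and 100%) alongside it, noting that it was prehospital and mostly cardiac arrest. Do not claim that capnography was shown to fall below a matched benchmark.

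The cost is one recalculated interval and rewording of a few paragraphs. No new data are needed.

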The median operating time of static post-intubation ultrasound was found to be 9 seconds with IQR [6 – 14 sec] by Chou et al²⁸ in their study. This was significantly faster than transcricothyroid static ultrasound for endotracheal tube confirmation done by Adi et al³⁰; their median time was 16.40 seconds. The results of these studies cannot be compared with this study because the beginning of laryngoscopy was taken as the start point for time assessment in this study. These studies started their assessment after intubation. The time for laryngoscopy is directly operator dependent and thus the time taken for assessment of endotracheal tube position directly increases with more time spent on doing laryngoscopy and intubation in this study.

Capnography

The sensitivity and specificity of capnography to detect endotracheal tube position was found to be 96.43% and 100% respectively in this study. This was similar to aggregate sensitivity and specificity of 93% and 97% found by Li in his meta-analysis.²⁴ This meta-analysis included trials which used any form of end tidal CO₂ detection device in adult human subjects. We have used only waveform capnography which is the gold standard; colorimetric and quantitative ET_{CO}₂ are less accurate than waveform capnography.^{3,7,8,12}

There were three false negative results in capnography. Two of the three false negative results occurred while using sidestream capnography at TUTH and the other false negative result occurred at MCVTC which also had sidestream capnography. There were more than two irregular waveforms during the first six ventilations in these false negative cases.

The false negatives might have occurred in the sidestream capnographs because these are more likely to be blocked due to fogging or misting^{2,7} such that the sampling line gas flow could have been obstructed. At MCVTC, after about 15 irregular waveforms, there was no waveform seen for about the next 90 seconds followed by presence of regular waveforms thereafter. This might be due to auto calibration of the capnograph, the occurrence of which during intubation might have produced false negative result.

Other causes like compromised pulmonary blood flow and bronchospasm can also lead to false negative results.^{3,9,10} Patients who had hypotension after induction of anaesthesia that could lead to compromised pulmonary flow, were excluded from this study. Bronchospasm would be identified by auscultation or high peak airway

pressure displayed in the ventilator. Bronchospasm had not occurred in any case during this study.

The median time for confirmation of tube position by capnography was 42 seconds. The maximum and minimum times were 67 seconds and 27 seconds respectively.

As discussed earlier, this time was dependent on the intubation time which was person dependent. To standardize the outcomes and time taken, literature was searched for rate of ventilations suggested during capnography measurement. No guideline or recommendation could be found. Most literature and textbooks have mentioned rates of 10 - 12 manual bag ventilations per minute during capnography.

The endotracheal tube in this study was connected after intubation to a preset ventilator with respiratory rate set at 26 ventilations per minute for standardization. This was excerpted from the study done by Pfeiffer et al³¹ who had used the same respiratory rate in their study for standardization. Using a fixed mechanical ventilation rate helped to study time for confirmation more precisely and reliably, as the performance of manual bag ventilations would be individual dependent. Individuals might perform manual bag ventilations faster or slower than the usual rates of bag ventilations. Individuals might deliver larger tidal volumes during manual bag ventilations which could be harmful. Using a fixed mechanical ventilation tidal volume also helped to avoid use of higher tidal volumes in this study.

A ventilation rate of 26 ventilations per minute helped to minimize bias in time taken for confirmation of endotracheal tube by capnography compared to ultrasonography. Using slower ventilation rates could have favoured the results towards ultrasonography being faster than capnography. In event of oesophageal intubation, a high ventilation rate could have led to more abdominal distension in the subjects.

However, during this study, subjects with initial oesophageal intubation did not have abdominal distension or high airway pressures when observed in the ventilator such that nasogastric tube decompression of the stomach would be required. This study had excluded patients at risk of aspiration of gastric contents, and also patients with known cardiopulmonary diseases in whom abdominal distension leading to difficulty in ventilation resulting in hypoxemia and hemodynamic compromise could have occurred.

This study used both sidestream and mainstream capnographs. This was because of availability of different types of capnograph at the study sites. The details of sampling line delay are discussed later.

Ultrasonography vs Capnography

Both ultrasonography and waveform capnography were found to be good, reliable and fairly accurate diagnostic methods of confirming endotracheal tube position. Though ultrasonography and capnography were equally sensitive and capnography seemed more specific; the sensitivity, specificity, PPV, NPV of ultrasonography were comparable (statistically not different as seen by their confidence intervals) to waveform capnography.

The combination of ultrasonography and capnography increased precision (accuracy) over using either one of them in this study. Since the studies done previously had compared ultrasonography against capnography as the standard and thus calculated the sensitivity, specificity, PPV, NPV of ultrasound; these were not able to show if ultrasound had increased accuracy over using capnography alone.

Both of these methods are now known to be equally reliable. Hence in case of unmatched result given by these two methods in a patient, a third highly reliable method of confirmation has to be used because both ultrasonography and capnography have statistically not different false positive (1 – specificity) and false negative (1 – sensitivity) rates.

There was generally good agreement between the results produced by ultrasonography and capnography as shown by the kappa value of 0.749 with 95% confidence interval of (0.567 – 0.931). Other studies have shown a good or a very good agreement of these two methods by kappa statistics. The kappa value calculated by Adi et al³⁰, Chou et al²⁸, Karacebay et al²⁷ and Chintamani et al³⁴ were 0.85, 0.93 (0.84 – 1.00), 0.85 and 0.76 respectively.

Real-time, transtracheal, transverse suprasternal ultrasonography was significantly faster ($p = 0.011$) than capnography by 16.36 ± 3.23 seconds (mean \pm SD) in confirming endotracheal tube position in this study. The subgroup analysis between mainstream and sidestream capnographs also showed that the type of waveform capnograph device used did not affect the significant difference in time of ultrasound over capnograph in confirming endotracheal tube position.

The sidestream capnograph at MCVTC had system response time of < 4 seconds, and that at TUTH had system response time of < 3 seconds. Adjusting for rise time of 200 milliseconds (the actual rise time of sidestream capnograph device used at TUTH; the rise time of that used at MCVTC was unknown), the transit time (delay time) would be in between 3 to 4 seconds in MCVTC sidestream capnograph and in between 2 to 3 seconds in TUTH sidestream capnograph. No delay was expected in mainstream capnograph device.

The median time taken for endotracheal tube confirmation by mainstream capnograph was 37 seconds and that by sidestream capnograph was 45.5 seconds. The combined median time taken for endotracheal tube confirmation by capnography was 42 seconds. The difference in time with ultrasonography was maximum of 19 seconds and minimum of 9 seconds while using mainstream capnograph, and maximum of 24 seconds and minimum of 12 seconds while using sidestream capnograph. These findings correlate to the delay time of sidestream capnographs as mentioned previously. Though theoretically the delay time should not have exceeded 4 seconds, the difference in median time for confirmation between these types of capnographs was 8.5 seconds. The median time for confirmation of endotracheal tube position in this study would be affected by the time taken by the anaesthesia resident for intubation. Thus difference in time for confirmation between the two types of capnographs could be greater or lesser than 8.5 seconds depending on the variability of time taken for intubation in this study.

Few studies have compared if ultrasound can be faster than capnography. Karacebay et al²⁷ found that dynamic transtracheal ultrasound at suprasternal level combined with lung sliding done by two separate operators simultaneously during intubation, was faster in average by 5.9 seconds than capnography for endotracheal tube confirmation. Pfeiffer et al³¹ found that lung ultrasound was in average 7.1 seconds faster than capnography in confirming endotracheal tube position.

The difference in time was greater in this study, likely due to use of sidestream capnograph. But as discussed earlier, this did not affect the significance in difference in time.

Chintamani et al³⁴ in their study comparing ultrasound and capnography found mean \pm SD time for confirmation by ultrasound to be 12 ± 1.31 secs, and that by capnography to be 8.98 ± 1.04 secs. Their finding of capnography being significantly faster is debatable because they used transtracheal ultrasound at suprasternal level first in transverse view then in longitudinal view, followed also by scanning towards the left side of neck to align the area of oesophagus towards the center of probe. They also have not mentioned the criterion for capnography, whether $ETCO_2$ values were used or not, and the number of waves they counted for a result.

LIMITATIONS

1. This study used both sidestream and mainstream capnographs as per availability at the study sites. Sidestream capnographs have a delay time in reading exhaled CO₂, which does not occur in mainstream capnographs.
2. Different persons (anaesthesia faculties with training in airway ultrasound) performed ultrasound imaging in this study.
3. This study did not see if novice ultrasound operators could also confirm endotracheal tube position by ultrasound imaging earlier than capnography.

CONCLUSION

Ultrasonography and waveform capnography are equally reliable and accurate methods of confirming endotracheal tube position. Confirmation of endotracheal tube position by real-time ultrasonography is faster than capnography independent of the ultrasound operator. The combination of ultrasonography with capnography in practice will help reduce time and increase precision of confirming endotracheal tube position.

RECOMMENDATIONS

- Real-time transtracheal ultrasonography is safe and can be used as an alternate method of confirming endotracheal tube position in operating theatres.
- Using real-time transtracheal ultrasound can help confirm endotracheal tube position earlier than capnography.
- Using real-time transtracheal ultrasound will help avoid manual bag ventilations to confirm endotracheal tube position and can prevent aspiration of gastric contents into lungs in cases of oesophageal intubation.

REFERENCES

